5.4. PK Analysis Set

The PK concentration population is defined as all treated patients who have at least 1 concentration of either of the study drugs.

The PK parameter analysis population is defined as all treated patients who have at least 1 of the PK parameters of interest of any of the study drugs.

5.5. Biomarker Analysis Set

The biomarker analysis population is defined separately for blood-based and tumor tissue-based biomarkers. The biomarker analysis population includes all enrolled patients who receive at least one dose of any study drug, and have at least one biomarker parameter from the corresponding assay sample with at least one baseline biomarker measurement. The following are the biomarker analysis sets for the purpose of specific PD biomarker analysis:

Serum biomarker analysis set,

Whole blood biomarker analysis set, and

Tumor biomarker analysis set.

5.6. Treatment Misallocations

Not applicable.

5.7. Protocol Deviations

All deviations will be described when they appear and relate to the statistical analyses or analyses populations.

6. ENDPOINTS AND COVARIATES

6.1. Efficacy Endpoints

Assessment of response will be made using RECIST version 1.1. All response statuses will be derived from lesion measurement data recorded on the electronic case report forms as provided by the investigator. .

Tumor assessments will include all known or suspected disease sites. Imaging may include chest, abdomen and pelvis CT or MRI scans; brain CT or MRI scan for patients with known or suspected brain metastases; bone scan for patients with known or suspected bone metastases.

The same imaging technique used to characterize each identified and reported lesion at baseline will be employed in the following tumor assessments.

Antitumor activity will be assessed through radiological tumor assessments conducted at baseline (screening), at 12 weeks, and every 6 weeks thereafter. In addition, radiological tumor assessments will also be conducted whenever disease progression is suspected (e.g. symptomatic deterioration) and at the time of withdrawal from the treatment (if not done in the previous 6 weeks).

- **Objective Response Rate (ORR)** is defined as the percent of patients with confirmed complete response (CR) or confirmed partial response (PR) according to the RECIST 1.1, relative to the response evaluable population. Confirmed responses are those that persist on repeat imaging study at least 4 weeks after initial documentation of response. Patients who do not have on-study radiographic tumor re-evaluation or who die, progress, or drop out for any reason prior to reaching a CR or PR will be counted as non-responders in the assessment of ORR. A patient who initially meets the criteria for a PR and then subsequently becomes a confirmed CR will be assigned a best response of CR.
- **Progression Free Survival (PFS)** is defined as the time from the date of first dose of MK-3475 (C1D1) to the date of the first documentation of objective tumor progression or death on-study due to any cause, whichever occurs first. If tumor progression data include more than 1 date, the first date will be used. PFS (in months) will be calculated as (first event date – first dose date +1)/30.44.

Patients lacking an evaluation of tumor response after the date of the first dose of MK-3475 (C1D1) will have their event time censored on the date of the first dose unless death occurs prior to 18 weeks (in which case the death is an event).

If patients have at least 1 on-study disease assessment, PFS data will be censored on the date of the last evaluable tumor assessment documenting absence of progressive disease for patients:

- Who are alive and progression free at the time of the analysis (note: summaries will distinguish between subjects still in disease follow-up versus those who have discontinued);

- Who have documentation of disease progression or death on study after ≥ 2 , consecutive missed tumor assessments (i.e. > 18 weeks for the first two assessments and then subsequently > 12 weeks after last tumor assessment);
- Who are given anti-tumor treatment other than the study medication prior to documented disease progression or death.

PFS (months) = [progression/death date – date of first dose +1]/30.44

- **Six-month progression-free survival (6m-PFS)** is summarized as a product limit estimator based on the Kaplan-Meier method to account for censored events.
- **Twelve-month progression-free survival (12m-PFS)** is summarized as a product limit estimator based on the Kaplan-Meier method to account for censored events.
- **Time to Response (TTR)** is defined as the time from first dose of MK-3475 (C1D1) to the first documentation of objective tumor response (CR or PR) that is subsequently confirmed. TTR will only be calculated for the subgroup of patients with a confirmed objective tumor response.

TTR (months) = [first date of OR – date of first dose +1]/30.44

- **Duration of Response (DR)** is defined as the time from first documentation of objective tumor response (CR or PR) until the first date that recurrent, progressive disease, or death due to any cause (whichever occurs first) is objectively documented. If tumor progression data include more than 1 date, the first date will be used. Censoring for DR is identical to the censoring rules presented for PFS. DR will only be calculated for the subgroup of patients with a confirmed objective tumor response.

DR (months) = [progression/death date – first date of OR +1]/30.44

- **Overall Survival (OS)** is defined as the time from the first dose of MK-3475 (C1D1) to the date of death due to any cause. OS will be summarized in the response evaluable population. For patients still alive at the time of the analysis, the OS time will be censored on the last date they were known to be alive. Patients lacking data beyond the day of first dose of study treatment will have their survival times censored at 1 day.

OS (months) = [date of death – date of first dose +1]/30.44

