## **9. DATA ANALYSIS/STATISTICAL METHODS**

Detailed methodology for summary and statistical analyses of the data collected in this trial will be documented in a Statistical Analysis Plan (SAP), which will be maintained by Pfizer. This document may modify the plans outlined in the protocol; however, any major modifications of the primary endpoint and/or its analysis will also be reflected in a protocol amendment.

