##### **9.4.1. Analysis of Efficacy Endpoints (Dose Expansion Phase Cohort)**

Objective response rate (ORR) is defined as the proportion of patients with a confirmed complete response (CR) or confirmed partial response (PR) according to RECIST version 1.1 definitions, relative to the response evaluable population. Confirmed responses are those that persist on repeat tumor assessments for at least 4 weeks after initial documentation or response. Otherwise, the patient will be counted as a non-responder in the assessment of ORR.

Time to Response (TTR) is defined as the time from first dose of study treatment to the first documentation of objective tumor response (CR or PR) that is subsequently confirmed.

Duration of Response (DR) is defined as the time from the first documentation of objective tumor response (CR or PR) that is subsequently confirmed to the first documentation of objective tumor progression or to death due to any cause, whichever occurs first.

Progression Free Survival (PFS) is defined as the time from the first dose of study treatment to the first progression of disease (PD) or death for any reason in the absence of documented PD. PFS will be summarized in the response evaluable population. PFS data will be censored on the date of the last tumor assessment on study for patients who do not have objective tumor progression and who do not die within 28 days of last dose. Patients lacking an evaluation of tumor response after enrollment will have their PFS time censored on the date of first dose with a duration of 1 day. Patients who are treated and removed from study

prior to on-study tumor assessment because of disease progression will be considered evaluable for efficacy and counted as an event at the time of progression. Additionally, patients who start a new anti-cancer therapy prior to documented PD will be censored at the date of the last tumor assessment prior to the start of the new therapy.

Overall Survival (OS) is defined as the time from the first dose of study treatment to the date of death due to any cause. OS will be summarized in the response evaluable population. For patients still alive at the time of the analysis, the OS time will be censored on the last date they were known to be alive. Patients lacking data beyond the day of first dose of study treatment will have their survival times censored at 1 day.

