1. AMENDMENTS FROM PREVIOUS VERSION(S)

- Specifies analyses of safety data (adverse events and laboratory tests) which includes the period from the start of treatment with the axitinib + MK-3475 combination (CD1).
- Clarified language regarding analysis sets for efficacy endpoints. Clarified that data from patients treated at the MTD in the dose escalation and dose expansion portions of the study will be pooled for the secondary safety and efficacy analyses.
- Removed supportive efficacy analysis.

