8.4. Summary of Secondary Efficacy Analyses

Endpoint	Analysis Population	Statistical Method	Missing Data	Analysis Type/Timing
ORR	Response Evaluable	Exact method based on F-distribution (95% CI) (See 8.3.2)	See Section 6.1	Secondary analysis
DR	Subgroup of pts with OR from the Response Evaluable	K-M method (median and 95% CI) (See 8.3.2)	See Section 6.1	Secondary analysis
TTR	Response Evaluable	Univariate (median and 95% CI) (See 8.3.2)	See Section 6.1	Secondary analysis
PFS	Response Evaluable	K-M method (median, 6 and 12m-PFS and 95% CIs) (See 8.3.2)	Censor patients on the day of the last evaluable tumor assessment documenting absence of disease progression for ... (See Section 6.1)	Secondary analysis
OS	Response Evaluable	K-M method (median and 95% CIs) (See 8.3.2)	See Section 6.1	Secondary analysis

CI: Confidence intervals; DR: Duration of Response; K-M: Kaplan-Meier; OR: Objective Response; ORR: Objective Response Rate; PFS: Progression-free Survival; TTR: Time to Response; OS: Overall Survival

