NOTE: Patients with a global deterioration of health status requiring discontinuation of treatment without objective evidence of disease progression at that time should be reported as "symptomatic deterioration." Every effort should be made to document the objective progression even after discontinuation of treatment. It should also be noted that a tumor marker increase does not constitute adequate objective evidence of tumor progression. However, such a tumor marker increase should prompt a repeat radiographic evaluation to document whether or not objective tumor progression has occurred.

In some circumstances, it may be difficult to distinguish residual disease from normal tissue. When the evaluation of complete response depends upon this determination, it is recommended that the residual lesion be investigated by fine needle aspirate or biopsy before confirming the complete response status.

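### SAP 6.1 drops, without saying so, the protocol's PFS event rule for progression before any scan, and its week limits censor some in-window progressions after one missed scan as if two had been missed

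*SAP*

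**What the plan says.** **Progression before any scan.** SAP 6.1 provides that patients with no tumor evaluation after C1D1 "will have their event time censored on the date of the first dose unless death occurs prior to 18 weeks". Protocol 9.4.1 has a similar general rule, censoring at first dose, but adds an exception: treated patients removed from study before an on-study tumor assessment "because of disease progression will be considered evaluable for efficacy and counted as an event at the time of progression". The SAP does not carry that exception over. Protocol section 9 says of the SAP: "This document may modify the plans outlined in the protocol". Only major changes to the primary endpoint or its analysis also need an amendment, and PFS is secondary. SAP 8.4 lists one PFS analysis: "K-M method (median, 6 and 12m-PFS and 95% CIs) (See 8.3.2".

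**Missed scans.** For patients with at least one on-study assessment, SAP 6.1 censors progression or death that follows two or more "consecutive missed tumor assessments (i.e. > 18 weeks for the first two assessments and then subsequently > 12 weeks after last tumor assessment". Censoring is at the last assessment showing no progression, and duration of response (DR) uses the same rules. Protocol 9.4.1 has no missed-assessment rule. Scans are due at week 12 and every 6 weeks thereafter. In the Schedule of Activities they sit in the Day 1 column for Cycles 2 onward, which carries a ±3-day window, and footnote 1 applies column windows to each assessment.

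**The concern.** A patient taken off study for progression before any scan leaves because of the very outcome that PFS measures. Censoring that patient at first dose is informative, and it gives a different result from the protocol for the same history. Since the SAP does not mention the change, a reader of both documents cannot tell whether it was intended.

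The missed-scan rule is stated as two or more misses but applied through limits that correspond to one. A progression actually seen on a compliant scan can then be discarded, and after an earlier clean scan the patient is censored about 12 weeks before it. In a single-arm trial no comparator is exposed to the same rule, so any upward shift stays in the reported PFS and DR.

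**Working it through.** **1. Progression before any scan**

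Inputs: up to 40 response-evaluable expansion patients (SAP 4.2), pooled with dose-finding patients treated at the MTD (SAP 8.3.2). At least 10 evaluable patients are required at that dose (SAP 8.1.1), so n is taken as about 50. Assumptions: true 12-month PFS of 50%, no other censoring before month 12, and k affected patients. The documents give no count for k.

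Moving k progressed patients to censoring at first dose changes the estimate from 25/50 to 25/(50 − k):
- k = 0: 50.0%
- k = 1: 25/49 = 51.0%
- k = 2: 25/48 = 52.1%

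With n = 40 and 12 events by month 6 (assumed), 6-month PFS moves from 28/40 = 70.0% to 28/39 = 71.8% (k = 1) or 28/38 = 73.7% (k = 2). Before the affected patient's own progression the curve falls trivially: after one earlier event, 49/50 = 98.00% becomes 48/49 = 97.96%.

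**2. Missed-scan limits**

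The SAP's limits reproduce from nominal dates: 12 + 6 = 18 weeks = 126 days, and 6 + 6 = 12 weeks = 84 days. Each is the date of the next scan after one miss. A scan exactly on schedule does not exceed the limit. With the ±3-day window:
- Week 12 missed, progression on the week-18 scan: in-window days are 126 ± 3 = 123 to 129. Days 127 to 129 are flagged as two misses.
- Last clean scan at week w, week w + 6 missed, progression on the week w + 12 scan: the in-window gap is 84 ± 6 = 78 to 90 days. Gaps of 85 to 90 days are flagged.
- Example: clean at week 12 (day 84), week 18 missed, progression at week 24 + 2 days (day 170). The gap is 86 days. The patient is censored at (84 + 1)/30.44 = 2.8 months instead of having an event at (170 + 1)/30.44 = 5.6 months.
- A scheduled scan after two true misses comes no earlier than 168 − 3 = day 165, or 126 − 6 = 120 days after the last scan. The flagged scans are therefore not double misses.

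Share flagged, given one miss just before progression (scan-day distribution assumed):
- Later scans: 21 of 49 day pairs = 43% if all seven days are equally likely. If 80% fall on the exact day and the rest are spread evenly, (1 − 0.64 − 6 × 0.0333²)/2 = 17.7%.
- Week 18: 3/7 = 43% or 10%.

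Effect per flagged progression at or after week 24: Kaplan-Meier simulation, 6,000 runs, n = 50, exponential PFS with a 12-month median, cut-off at 18 months, one such progression moved to censored 84 days earlier.
- Progression by month 12 (60.8%): +1.459 points on 12-month PFS
- Gap straddling month 12 (18.1%): −0.077
- Later (21.1%): 0
- Average: 0.608 × 1.459 − 0.181 × 0.077 = +0.87

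Total = progressions × miss rate × share flagged × effect, with 21.7 such progressions per trial and an assumed miss rate of 2 to 10%:
- Low: 21.7 × 0.02 × 0.177 × 0.873 = 0.07 points
- High: 21.7 × 0.10 × 0.429 × 0.873 = 0.81 points

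Week-18 progressions (3.3 per trial) can be added only by assuming censoring at first dose, worth +1.076 points each. The range is then 0.07 to 0.96. The sampling SD of 12-month PFS in the simulation was 7.0 points.

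**The case against.** The SAP is entitled to make this change and is coherent in doing so. It defines PFS by objective progression derived from lesion measurements, and Appendix 3 separates symptomatic deterioration from objective progression. The affected group is small by design: "radiological tumor assessments will also be conducted whenever disease progression is suspected", a scan is also required at withdrawal from treatment if none was done in the previous 6 weeks, and Appendix 3 adds "Every effort should be made to document the objective progression even after discontinuation of treatment". An affected patient must have neither scan after C1D1 and must not die before 18 weeks. All of this stands. It leaves an unstated departure of narrow reach.

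A reader might take the SAP's amendment list, with its entry "Removed supportive efficacy analysis", as evidence that the change was concealed or that a PFS sensitivity analysis was deleted. The list records changes between SAP versions, not departures from the protocol, and does not say what the removed analysis covered.

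A reader might also infer that no output would reveal the difference. SAP 8.3.2 lists progression, death, last-assessment and dosing dates beside PFS, and SAP 8.3.1 lists discontinuation reasons. With about 50 patients, individual cases could be found.

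On the second rule, the obvious repair of widening the later limit to a flat 90 days has its own fault. If the last scan was 3 days late (D + 3), the next two windows close at D + 45 and D + 87. A death or unscheduled progression scan at D + 88 to D + 93 is 85 to 90 days after that scan and follows two true misses. The 84-day limit censors it correctly and a 90-day limit would not. This stands, and it is why the fix should count windows.

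**Conclusion.** Both points hold, with modest weight. The first is a permitted but undeclared departure that makes censoring informative for a narrow group: about 1 point on 12-month PFS per affected patient, for n = 50 and PFS of 50%. The second is a rule that contradicts its own two-miss wording in identifiable cases, in PFS and DR. Its total effect is probably under 1 point on 12-month PFS, against a sampling SD of about 7. That size rests on assumed miss rates, scan-day distributions and an exponential PFS curve, none of which the documents give, and on scan weeks counted from C1D1.

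The documents do not support a claim that the SAP broke the protocol or that reported PFS would be materially inflated. Nor can +1.1 points be taken as settled for a week-18 progression after a missed week 12. The first-dose rule covers only patients with no evaluation, and this patient has one. The other rule points to the last assessment showing no progression, and none exists after baseline. The SAP leaves that censoring date undefined.

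**What to change.** In SAP 6.1:
1. State that progression without an on-study scan is not counted as in protocol 9.4.1. Keep the objective-progression analysis if preferred, and add a PFS sensitivity analysis counting these patients as events on the recorded progression date. Restoring the protocol rule is the alternative.
2. Define a missed scheduled assessment as one whose visit window closes without a scan, and apply the two-miss rule to that count in PFS and DR. For the first two assessments this equals more than 129 days from C1D1. Do not use a flat gap for later scans.
3. Align the 18-week cut-off for deaths without any scan with the same rule.
4. State the censoring date when no post-baseline scan shows absence of progression.

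The cost is SAP wording, one extra table and some programming of visit windows. Recorded clinical progression dates are less objective than scan dates, and PFS may look slightly less favorable.

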6.2. Safety Endpoints

6.2.1. Dose Limiting Toxicity (DLT) (Primary Endpoint for Dose Finding Cohorts)

Severity of AEs will be graded according to NCI CTCAE v 4.03. AEs meeting one of the definition criteria in protocol Section 3.1.2 occurring in the DLT observation period (6 weeks post C1D1) which are attributable to one or both study drugs will be classified as DLTs.

6.2.2. Adverse Events

AEs will be characterized by type, frequency, severity (as graded by NCI CTCAE version 4.03), timing, seriousness and relationship to study treatment. Adverse events occurring during the 7 day lead in phase for PK will be summarized separately from adverse events reporting after first dose of MK-3475 (C1D1). Baseline signs and symptoms will be recorded at baseline and then reported as adverse events during the trial if they worsen in severity or increase in frequency.

Treatment Emergent Adverse Events

All deaths and serious AEs, regardless of cause, occurring from start of treatment until 28 days after the last dose will be considered treatment-emergent. All other non-serious AEs occurring after treatment start regardless of cause, will be considered treatment-emergent up until 28 days after the last dose or until start of new anti-cancer treatment, whichever occurs first. Disease progression is not considered a treatment emergent AE unless the patient dies of disease prior to 28 days after the last dose. Events that are continuations of baseline abnormalities are considered treatment emergent AEs only if there is an increase in grade over baseline, or if there is an increase following a decrease during the study.

For subjects with a 7 day lead-in phase for PK, adverse events reported during the lead-in phase will only be considered as treatment emergent for the combination if there is an increase in grade after the first dose of MK-3475 (C1D1) or if there is a decrease and then subsequent increase during treatment with the combination.

Treatment Related Adverse Events

Treatment emergent AEs with causality related to treatment, as judged by the investigator, will be considered treatment-related. Events that are continuation of baseline abnormalities are not considered treatment- related unless there is an increase in grade, or if there is an increase following a decrease, and the increase is judged by the investigator to be due to treatment.

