19. **Adverse Events:** Adverse events should be documented and recorded at each visit using NCI CTCAE version 4.03. For SAEs, the active reporting period to Pfizer or its designated representative begins from the time that the patient provides informed consent, which is obtained prior to the patient's participation in the study, ie, prior to undergoing any study-related procedure and/or receiving investigational product, through and including 90 calendar days after the last administration of the investigational product and before initiation of a new anti-cancer treatment. The prolonged follow up is due to the pharmacokinetic properties of the investigational product MK-3475. SAEs experienced by a patient after the active reporting period (see [Section 8.1.1](#)) has ended should be reported to the Sponsor if the Investigator becomes aware of them; at a minimum, all SAEs that the Investigator believes have at least a reasonable possibility of being related to study drug are to be reported to the Sponsor. AEs (serious and non serious) should be recorded on the Case Report Form (CRF) from the time the patient has taken at least one dose of study treatment through last patient visit (Day 28 after last dose). If a patient begins a new anticancer therapy, the AE reporting period for non serious AEs ends at the time the new treatment is started. Pregnancy or breast feeding that occur during the trial, within 120 days of discontinuing treatment with MK-3475, or within 28 days after the cessation of study treatment if the patient begins a new anticancer therapy, whichever is earlier, should be reported as in [Section 8.4 \(Exposure During Pregnancy\)](#).

20. **Concomitant Medications/Treatments:** Concomitant medications and treatments will be recorded from 28 days prior to the start of study treatment and up to 28 days after the last dose of study treatment. All concomitant medications should be recorded in the CRF including supportive care drugs (eg, anti-emetic treatment and prophylaxis), and the drugs used to treat adverse events or chronic diseases, and non-drug supportive interventions (eg, transfusions).

21. **Registration:** Patient number and dose level allocation operated by Pfizer Inc. Required information: site and patient identifiers and demographic information. Study treatment (either single agent axitinib for patients in Lead-in or axitinib in combination with MK-3475 for all other patients) should begin within 7 days of registration.

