## **9.6. Safety Analysis**

Summaries and analyses of the primary safety endpoint will be based on the per protocol analysis set. All other summaries and analyses of safety parameters will include all patients in the Safety Analysis Set. Safety data will be summarized by each cohort for all treated patients using appropriate tabulations and descriptive statistics. Safety data collected during the lead-in PK period will be reported separately. The analysis of safety will extend through 90 days after the last administration of study drug.

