8.3.3.2. Analysis of Secondary Safety Endpoint

Adverse Events

AEs will be graded by the Investigator according to the Common Terminology Criteria for Adverse Events (NCI CTCAE) version 4.03 and coded using the Medical Dictionary for Regulatory Activities (MedDRA). The focus of AE summaries will be on treatment-emergent AEs. The number and percentage of patients who experienced any AE, serious AE (SAE), treatment-related AE, and treatment-related SAE will be summarized according to worst toxicity grades. The summaries will present AEs on the entire study period, separately for the lead-in PK period and by cycle (Cycle 1, Cycle 2 and Cycles beyond 2), as well as for the entire treatment period starting at C1D1 (first dose of MK-3475).

For AE summaries of the treatment period starting at C1D1, treatment-emergent will be defined as an adverse event with an initial onset or increasing severity after the first dose of

MK-3475. For all other AE summaries, treatment-emergent will be defined as an adverse event with an initial onset or increasing severity after the first dose of any study medication (axitinib, in the case of the lead-in PK period).

- An overall summary of AEs will be provided. The number and percentage of patients who experienced any AE, who experienced any SAE, who experienced any treatment-related AE, who experienced any treatment-related SAE, and who discontinued because of an AE will be presented. Treatment-related AEs are those judged by the investigator to be at least possibly related to the study drug (with a cause related to the study drug indicated on the CRF).
- All treatment-emergent AEs will be summarized by MedDRA SOC and preferred term. A summary of AEs by preferred term and maximum CTCAE grade will be presented. A summary of AEs by preferred term and maximum CTCAE grade group (Grade 1-2, Grade 3-4, and Grade 5) will also be presented. Treatment-emergent AEs will also be summarized for each group and pooled across the groups.
- Treatment-related AEs will be summarized by MedDRA SOC and preferred term separately for axitinib, MK-3475 and both. A summary of treatment-related AEs by preferred term and maximum CTCAE grade will be presented. A summary of treatment related AEs by preferred term and maximum CTCAE grade group (Grade 1-2 vs. Grade 3-5) will also be presented. Treatment-related AEs will also be summarized for each group and pooled across the groups.

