- Deaths will be summarized by three time periods (on-treatment vs. within 90 days of end of treatment vs. > 90 days after end of treatment) and cause of death. Deaths that occurred within 28 days after the last dose of study treatment are defined as on-treatment deaths. Death data will also be listed.
- Patients who withdraw from study treatment because of an AE will be listed separately for axitinib and MK-3475. Patient discontinuation will be determined from the end of treatment (EOT) evaluation (where reason for termination is “Adverse Event”) and the specific AE(s) will be determined from the AE CRF page (where action taken is “Withdrawn from Treatment”).
- SAEs and treatment-related SAEs will be summarized by MedDRA SOC and preferred term. Patients who experienced a SAE will be listed.

The following analyses will be performed for AEs of special interest (including, but not limited to, hepatic disorders [ALT, AST and bilirubin], thyroid dysfunction [hypo-/hyperthyroidism], diarrhea, colitis and pneumonitis).

- Hy's Law eDISH scatterplot of Maximum ALT vs. Maximum Total Bilirubin on treatment.

- Hy's Law eDISH scatterplot of Maximum AST vs. Maximum Total Bilirubin on treatment.
- The prevalence of AEs of special interest will be summarized by preferred term and maximum CTC severity grade.
- Descriptive statistics will be presented for time to AE onset (days), time to grade 2 and grade 3/4 AE onset.

For all safety analyses, only descriptive methods will be used without any formal statistical test.

Laboratory Tests

The number and percentage of patients who experienced laboratory test abnormalities will be summarized according to worst toxicity grade observed for each lab assay. The analyses will summarize laboratory tests on the entire treatment period, separately for the lead-in PK period and by cycle (Cycle 1, Cycle 2 and Cycles beyond 2), as well as for the entire treatment period starting at C1D1 (first dose of MK-3475) for patients receiving combination therapy.

For laboratory tests without CTC grade definitions, results will be categorized as normal, abnormal or not done.

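### SAP 6.2.2 ends treatment-emergent status 28 days after the last dose, protocol 9.6 carries the safety analysis to 90 days, and the SAP does not reconcile the two

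*SAP*

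**What the plan says.** **SAP 6.2.2** sets the end of the treatment-emergent window: "All deaths and serious AEs, regardless of cause, occurring from start of treatment until 28 days after the last dose will be considered treatment-emergent". Non-serious events have the same 28-day limit, or the start of new anticancer treatment if that comes first. The section then builds the related category on top: "Treatment emergent AEs with causality related to treatment, as judged by the investigator, will be considered treatment-related".

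**Protocol 9.6** says: "The analysis of safety will extend through 90 days after the last administration of study drug". Its definition of treatment-emergent, in 9.6.2.1, gives a starting point and no end date. Footnote 19 to the Schedule of Activities gives the reason for the 90-day SAE period: "The prolonged follow up is due to the pharmacokinetic properties of the investigational product MK-3475".

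**SAP 8.3.3.2**, which specifies the tables, defines both terms again. Outside the period starting at Cycle 1 Day 1, "treatment-emergent will be defined as an adverse event with an initial onset or increasing severity after the first dose of any study medication". The definition for that period also has a start and no end. The section describes treatment-related events by investigator judgement alone, without requiring them to be treatment-emergent and without an end date.

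**The only 90-day window in the SAP** is in the death table of 8.3.3.2: "on-treatment vs. within 90 days of end of treatment vs. > 90 days after end of treatment".

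**Collection.** Protocol 8.1.4 to 8.1.4.2 collect AEs and SAEs for at least 90 days. SAEs are kept after new anticancer therapy, and non-serious recording stops when it starts. Footnote 19 and Appendix 6 footnote 12 instead end CRF recording of AEs at the Day 28 visit and limit active SAE reporting to the time before new therapy.

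**The concern.** The protocol commits to a 90-day safety analysis and ties the long SAE follow-up to how slowly MK-3475 clears. Section 5.2.7.4 adds that immune-related events can appear months after the last pembrolizumab dose. The SAP makes treatment-emergent events the focus of its AE summaries and closes that category at 28 days. SAEs that sites must report up to day 90 can therefore be collected and still fall outside the main AE tables.

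The overall safety profile of the combination is a secondary objective. Late immune-related toxicity is the kind of event that the longer window was meant to catch. With two definitions of each term in the SAP, two programmers could also build different tables from the same data.

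**Working it through.** The SAP gives no figure to reproduce. The check sets the texts side by side and sizes the gap.

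**1. Length of the gap.** Protocol window 90 days (9.6), SAP window 28 days (6.2.2). 90 − 28 = 62 days; 62/90 = 69% of the protocol's post-treatment window.

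**2. Which outputs are cut at 28 days.**
- Treatment-emergent AE tables: yes, under 6.2.2.
- Treatment-related AE and SAE tables: yes if 6.2.2 governs, no if 8.3.3.2 governs. The SAP does not say which.
- Overall SAE summary and SAE listing: not expressly cut. The text is "SAEs and treatment-related SAEs will be summarized by MedDRA SOC and preferred term".
- Special-interest prevalence and time to onset (8.3.3.2; prevalence rules in SAP Appendix 1): not expressly cut.
- Deaths: tabulated beyond 90 days.
- DLTs: 6-week observation period, unaffected.

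**3. MK-3475 still present.** Half-life 21–28 days (protocol 3.1). Fraction remaining = 0.5^(t / half-life), with t counted from the last infusion.
- t = 28: 0.5^(28/21) = 0.397 and 0.5^(28/28) = 0.50, so 40–50%.
- t = 90: 0.5^(90/21) = 0.051 and 0.5^(90/28) = 0.108, so 5–11%.

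These figures apply only if MK-3475 was given up to the last study dose. Protocol 3.1 lets axitinib continue alone. If the last axitinib dose came 21 days after the last infusion (an assumed interval), day 28 is 49 days after that infusion: 0.5^(49/21) = 0.20 to 0.5^(49/28) = 0.30. Longer axitinib monotherapy leaves less.

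**4. Sensitivity of the tables.** About 60 patients are planned, so one patient is 1/60 = 1.7 percentage points, and only if that patient had no earlier event of that type. For illustration, take the single-agent MK-3475 rates in protocol 1.2.2.4:
- Any AE, 97.3–98.8%: patients without one = 60 × 0.027 = 1.6 to 60 × 0.012 = 0.7. This row can hardly move.
- Drug-related SAE, 6.7–9.3%: 60 × 0.067 = 4.02 to 60 × 0.093 = 5.58 patients. One more adds 1/4.02 = 25% to 1/5.58 = 18% in relative terms. This matters only if 6.2.2 governs, and higher combination rates would make it smaller.

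**5. Collection.** The post-treatment visit falls on days 28–35 (Schedule of Activities, footnote 4). A site that followed footnote 19 or 12 would stop CRF recording of AEs there. A site that followed 8.1.4.2 would continue to at least day 90, with non-serious AEs ending earlier if new therapy started.

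**The case against.** The strongest reply has four parts.

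- **The SAP is allowed to differ.** Protocol section 9 lets the SAP modify planned analyses and asks for a protocol amendment only for major changes to the primary endpoint or its analysis. This stands: the difference is not forbidden. But the permission does not reconcile two stated windows, and the SAP never says that it departs from 9.6.
- **8.3.3.2 may already be broad enough.** Its open-ended treatment-emergent wording follows protocol 9.6.2.1, and its related definition has no cut-off. This stands in part. A reader might infer from 6.2.2 that late drug-related events certainly leave the treatment-related tables. The documents do not support that, because they do not say which section governs. Nor does 8.3.3.2 supply a 90-day end date.
- **The 28 days match the protocol's footnotes 19 and 12.** True, so part of the problem lies in the protocol. Yet footnote 19 itself keeps active SAE reporting to day 90 unless new therapy starts, so late SAEs are collected on either reading.
- **Other outputs catch late events.** The SAE summary and listing, the special-interest analyses and the death table may do so, and protocol 7.1.2.1 requires events of clinical interest to be reported through 90 days or until new therapy. This limits the harm. It does not restore a 90-day treatment-emergent analysis.

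A reader might also infer that the SAP shortened a window the protocol had already fixed. No SAP date is visible, so the order of the two texts cannot be established. The SAP's amendment list records changes between SAP versions, so its silence on this point shows nothing about differences from the protocol.

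**Conclusion.** The plan is wrong as written on this point. SAP 6.2.2 and protocol 9.6 give different ends to the safety window, 28 against 90 days, and nothing in the SAP reconciles them. Under 6.2.2, non-fatal events on days 29–90 are excluded from the treatment-emergent tables. Their exclusion from the treatment-related AE and SAE tables is conditional on 6.2.2 overriding 8.3.3.2.

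The size of the effect on results is unknown, since the documents give no late-event rate. The 18–25% figure describes one hypothetical patient at single-agent rates under the conditional reading; it is not an estimate of bias. The 40–50% residual likewise assumes MK-3475 up to the last study dose. The consequence is confined to descriptive secondary safety reporting, but the correction is cheap and uses data that protocol 8.1.4 already requires.

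**What to change.** 1. Add AE, SAE, treatment-related AE and treatment-related SAE summaries through 90 days after the last dose of study treatment. State the anchor explicitly, for example the later of the two drugs. End non-serious AEs at new anticancer therapy; keep SAEs after new therapy and flag them. The 28-day tables may stay alongside, with the difference from protocol 9.6 stated in the SAP.
2. Use one definition of treatment-emergent and one of treatment-related, each with an end date, in both 6.2.2 and 8.3.3.2.
3. Reconcile footnotes 19 and 12 with protocol 8.1.4 to 8.1.4.2 on the recording period and on new therapy. Footnote the 90-day tables to say that non-serious AEs on days 29–90 may be incompletely recorded.
4. When adding the longer window, check this sentence of SAP 6.2.2 against protocol 8.2.3: "Disease progression is not considered a treatment emergent AE unless the patient dies of disease prior to 28 days after the last dose". Protocol 8.2.3 ties reporting of fatal progression to the safety reporting period, so a 90-day window could bring more disease deaths into the AE tables.

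The cost is SAP and footnote wording, one extra set of tables and an SAE flag. The 90-day tables may show uneven capture of late non-serious AEs, which the footnote in step 3 would disclose.
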